## 6.3 Comparator population

The comparator population will be the matched historical controls and the patients randomised to BAC only.

#### 6.4 Safety population

The safety population will be all patients randomised to either BAC + dornase alfa or BAC only.

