8.8 Discontinuation/withdrawal of participants

In consenting to participate in the trial, participants are consenting to trial treatment, assessments, follow-up and data collection.

Discontinuation of trial treatment for clinical reasons

A participant may be withdrawn from trial treatment whenever continued participation is no longer in the participant's best interests, but the reasons for doing so must be recorded. Reasons for discontinuing treatment may include:

- Alternative clinical diagnosis emerges (no longer considered to have primary COVID-19 lung disease).
- Disease progression whilst on therapy.
- Unacceptable toxicity.
- Intercurrent illness which prevents further treatment.
- Patients withdrawing consent to further trial treatment.
- Any alterations in the participant's condition which justifies the discontinuation of treatment in the Cl's or designee's opinion.
- Persistent non-compliance to protocol requirements.
- Participant is put on end of life pathway and dies prior to dosing.

The decision to withdraw a participant from treatment must be recorded in the CRF and medical notes, and the sponsor when required should be notified in writing.

Participant withdrawal from trial treatment or follow-up

If a participant expresses their wish to withdraw from trial treatment or follow-up, sites should explain the importance of remaining on trial follow-up and seek permission to allow use of routine follow-up data to be used for trial purposes. The importance of safety follow-up should be emphasised to the participant in the Participant Information Sheet.

The decision of the participant to withdraw from treatment or follow-up must be recorded in the CRF and medical notes.

The participant may withhold their reason for withdrawal however, if the participant gives a reason for their withdrawal, this should be recorded.

Withdrawal of consent to data collection

If a participant explicitly states that they do not wish to contribute further data to the trial their decision will be respected and recorded in the CRF and medical notes.

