11.3 Statistical analysis plan

11.3.1 Summary of baseline data and flow of participants

All subjects enrolled in the study will be accounted for in a CONSORT diagram. There will be multiple analysis populations:

1 Primary analysis population - all evaluable patients randomised to dornase alfa + matched historical comparators.

2 Per protocol population - as above but excluding protocol violations.

3 Safety population - all enrolled patients receiving at least one dose of dornase alfa and the comparator groups.

4 Comparator population - the matched historical controls, patients randomised to BAC and historical records linked to biobanked samples.

5 Exploratory analysis population - all evaluable patients randomised to dornase alfa or to BAC plus historical patient data from biobanked samples.

The primary analysis will be conducted using the primary analysis population and is based on the ITT principle. Details on subjects enrolled but not included in the analysis populations will be presented as part of the CONSORT diagram.

The key baseline data that will be used to compare the groups and the analysis populations are age, gender, BMI, baseline CRP, oxygen requirements and the number of comorbidities. In general, continuous data will be summarised using the mean, standard deviation, median, minimum and maximum and categorical data will be represented as frequency counts and percentages.

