#### 11.4 Safety analyses

Safety of dornase alfa will be assessed by comparisons of adverse events (AEs), serious adverse events (SAEs), treatment-emergent adverse events (TEAEs) and deaths. The safety population is defined in Section 6.4.

All AEs will be summarized by BAC + dornase alfa/BAC only. A TEAE is an AE that starts or worsens at any time after initiation of study drug on Day1 through to end of follow-up.

For SAEs occurring in  $\geq$ 5% of individuals, follow-up-adjusted event rates based on events by randomised arm will be provided. The rates will be calculated as the total number of events in the randomised arm divided by the total sum of days follow-up in that randomisation arm, multiplied by 365.25, to give the expected number of events per patient year.

Listings of all TEAEs and SAEs will be provided.

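### SAP 6.4 drops the protocol's at-least-one-dose condition from the safety population, so any never-dosed dornase alfa patient stays in that arm's adverse event denominators

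*SAP*

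**What the plan says.** The two documents define the safety population differently.

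- Protocol 11.3.1: "Safety population - all enrolled patients receiving at least one dose of dornase alfa and the comparator groups".
- SAP 6.4: "The safety population will be all patients randomised to either BAC + dornase alfa or BAC only".

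Protocol 8.2 treats a participant as enrolled only once randomisation and allocation are complete. The dose condition in the protocol is therefore a real narrowing of the randomised set, and the SAP removes it. The SAP's audit trail does not mention the change.

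SAP 11.4 then uses this population throughout: "Safety of dornase alfa will be assessed by comparisons of adverse events (AEs), serious adverse events (SAEs), treatment-emergent adverse events (TEAEs) and deaths", followed by "The safety population is defined in Section 6.4". AEs are grouped by arm: "All AEs will be summarized by BAC + dornase alfa/BAC only". For the more frequent SAEs, a rate is formed as events "divided by the total sum of days follow-up in that randomisation arm". The treatment-emergent definition does depend on exposure: "A TEAE is an AE that starts or worsens at any time after initiation of study drug on Day1 through to end of follow-up".

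Protocol 8.8 includes this among the reasons for stopping trial treatment: "Participant is put on end of life pathway and dies prior to dosing". Protocol 9.4 records SAEs from randomisation.

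**The concern.** A safety population normally describes people exposed to the drug. Here the active group can include people who received none. Two consequences follow.

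- A never-dosed patient cannot have a TEAE but is still counted in the TEAE denominator, so the proportion with events is pulled down.
- An AE or SAE that occurs between randomisation and a first dose that never comes, if recorded, appears under dornase alfa.

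The protocol's risk section describes this as the first use of the drug in COVID-19 and allows that tolerability may differ from that in cystic fibrosis. With about 30 patients planned on the drug, the tables should state clearly who was exposed. The two definitions also disagree about historical comparators: the protocol's wording brings in the comparator groups, while SAP 6.4 covers randomised patients only.

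**Working it through.** No figure in the plan depends on the safety population, so there is none to reproduce. The check is a comparison of definitions, followed by denominator arithmetic.

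**Step 1. Where a never-dosed patient in the dornase alfa arm is counted under SAP 6.4 and 11.4**

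| Summary | Can be in the numerator? | In the denominator? |
|---|---|---|
| TEAEs | No, study drug never started | Yes |
| All AEs | Yes, if a pre-dose event is recorded | Yes |
| SAEs | Yes, if recorded (the window opens at randomisation) | Yes |
| SAE rate per patient-year | Yes, if recorded | Yes, through the arm's total follow-up days |
| Deaths | Yes | Yes |

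Under the protocol definition the same patient is in none of these rows on the active side.

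**Step 2. Inputs**

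- N = 30 planned on dornase alfa (Protocol 5.1, SAP 3), and N = 36 at the maximum after re-estimation (SAP 12).
- k = number randomised to dornase alfa and never dosed. The documents do not give it. Assumed range: 0 to 3.
- Event risk in dosed patients: 20%, assumed for illustration.

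**Step 3. Dilution of AE proportions**

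If never-dosed patients contribute no events, the reported proportion is the proportion in dosed patients × (N − k)/N.

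| k | Factor, N = 30 | 20% is reported as | Factor, N = 36 | 20% is reported as |
|---|---|---|---|---|
| 0 | 1.000 | 20.0% | 1.000 | 20.0% |
| 1 | 29/30 = 0.967 | 19.3% | 35/36 = 0.972 | 19.4% |
| 2 | 28/30 = 0.933 | 18.7% | 34/36 = 0.944 | 18.9% |
| 3 | 27/30 = 0.900 | 18.0% | 33/36 = 0.917 | 18.3% |

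**Step 4. Events not seen at all**

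The 95% upper bound for zero events is 1 − 0.05^(1/n). With n = 30 it is 9.5%. With n = 27 dosed it is 10.5%.

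**Step 5. SAE rate per patient-year**

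Assume 2 SAEs in dosed patients and 35 days of follow-up for everyone.

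- All 30 randomised: 2/(30 × 35) × 365.25 = 0.70.
- 27 dosed: 2/(27 × 35) × 365.25 = 0.77.

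**Step 6. Deaths**

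If all k never-dosed patients died before dosing, they would account for k/30 of the arm's death proportion: 3.3, 6.7 or 10.0 percentage points for k = 1, 2 or 3. This is what an all-randomised comparison is meant to show. Early deaths on BAC are counted in the same way.

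**The case against.** A reader might infer something stronger: that pre-dose deaths will be charged to the drug and that reaction rates will be materially understated. The documents do not support that.

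- Counting by arm is not attribution. Protocol 9.3.2 has causality judged for each event, and an event before any dose would have no plausible link to the drug.
- The TEAE definition already keeps pre-dose events out of TEAE counts. Only the denominator is affected.
- Protocol 9.2, 9.4 and 9.5 keep anticipated COVID-19 events, including death, out of the CRF and the SAE log. A pre-dose COVID-19 death would normally not reach the AE or SAE tables.
- The item in Protocol 8.8 sits in a list of reasons for discontinuing treatment and could mean death before a further dose. Eligibility is confirmed on Day 1, the first dosing day, and staff administer the drug, so never-dosed patients may be few or none.
- The 4–15% mortality in Protocol 3 is background for confirmed COVID-19 pneumonia, not an assumption about this trial's arm, so it cannot be used to derive expected deaths here.

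For deaths, the all-randomised set is the better choice. BAC has no placebo and no first dose. Removing early deaths from the dornase alfa side while keeping all of them on the BAC side would favour the drug.

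The protocol also defers analysis detail to the SAP, and Protocol 11.5 requires deviations from the statistical plan to be justified in the final report. The SAP's table shells are in a separate file that is not available here and may handle some of this.

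These arguments limit the harm. They do not remove the unexplained conflict between the two definitions or the exposure-dependent TEAE count over a denominator that ignores exposure. SAP 10.1 counts those who discontinued dornase alfa for any reason, which does not identify those who never started.

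**Conclusion.** The point holds as a mismatch of definitions with a bounded effect. Under SAP 6.4 and 11.4 as written, a never-dosed patient remains in the drug arm's AE, SAE and TEAE denominators, and any recorded pre-dose AE or SAE counts in that arm. If 1 to 3 of 30 were never dosed, and they contribute no events, AE proportions shrink by 3.3% to 10.0% in relative terms. At an assumed 20% risk that is 0.7 to 2.0 percentage points. Recorded pre-dose events would push the all-AE and SAE figures the other way. If everyone is dosed, nothing changes. The size rests entirely on the assumed number never dosed. The separate omission of historical comparators from the safety set does not depend on that number and also needs a statement.

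**What to change.** Reconcile SAP 6.4 with Protocol 11.3.1 and bring SAP 11.4 into line:

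1. For AE, TEAE and SAE summaries and rates, compare participants who received at least one dose of dornase alfa with all participants randomised to BAC who received none.
2. Replace the randomised-arm wording for SAE rates in SAP 11.4, so that events and follow-up days come from these same groups.
3. In SAP 10.1, add the number randomised to dornase alfa but never dosed, and list their events separately. They belong to neither group in item 1 and would otherwise disappear.
4. Keep the comparison of deaths by randomised arm, with all randomised participants included and any pre-dose deaths flagged.
5. State whether the historical comparators are part of the safety population and, if they are not, why the SAP departs from the protocol.

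The cost is SAP text and small changes to the table shells. No new data are needed for items 1 to 4: dispensing is logged (Protocol 6.4) and inhalation is observed and recorded (Protocol 8.7). If the sponsor prefers to keep the all-randomised definition throughout, the SAP should give the reason and still include item 3.

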## 6.5 Exploratory analysis population

The exploratory analysis population will be all evaluable patients randomised to BAC + dornase alfa or to BAC only, plus historical patient data from biobanked samples.

## **Exploristics** Limited

#### CONFIDENTIAL

Identifier: EXP20012 Clinical Study Identifier: 132333

#### 7. TREATMENT COMPARISONS

The primary treatment comparison will be between individuals randomised to BAC + dornase alfa and the comparator population.

However, comparisons will also be made between the groups forming the comparator population, namely the patients randomised to BAC only and the matched historical controls. These analyses will quantify how similar the matched historical control population is to the participants randomised to BAC only, see section 8.3.1 for details.

## 8. GENERAL CONSIDERATIONS FOR DATA ANALYSES

## 8.1 Dependent Variables (Endpoint Variables)

For the primary endpoint analysis, the dependent variable will be CRP levels.

#### 8.2 Independent Variables

For the primary endpoint analysis, the independent variables included in the model will be treatment (dornase alfa vs. no dornase alfa), age, gender, BMI, baseline CRP level (defined as the last CRP value prior to randomisation, or the first CRP following Dexamethasone for HCs), time from baseline and whether they have a key comorbidity, defined as one or more of hypertension, diabetes or cardiovascular disease. An interaction term between treatment and time from baseline will also be included in the model.

For secondary endpoint analyses, the same covariates will be included in the models as for the primary endpoint analysis.

#### 8.3 Examination of Subgroups

#### 8.3.1 Primary endpoint analyses

At the interim and final analyses, the primary analysis will be to combine the two sets of individuals on BAC only in the comparator population to the individuals randomised to BAC + dornase alfa.

However, three additional analyses will be carried out at the final analysis for the primary endpoint analysis.

- 1. A comparison of the BAC + dornase alfa arm to those randomised to BAC only (no historical controls)
- 2. A comparison of the BAC + dornase alfa arm to matched historical controls (no individuals randomised to BAC only)
- 3. A comparison of those randomised to BAC only to matched historical controls (within control comparison).

The treatment effect estimate will be compared between the primary analysis and analyses 1. and 2. above. No formal test will be carried out to test the difference in treatment effect between the three analyses, but substantial differences will be noted.

### **Exploristics Limited**

### Identifier: EXP20012 Clinical Study Identifier: 132333

In analysis 3., no treatment effect will be included in the model, since all individuals are on BAC only. Instead, a covariate will be included to indicate whether the individual is a historical control or a randomised individual.

In addition, analyses stratified by BAC treatment will be carried out for the primary endpoint.

### 8.3.2 Secondary endpoint analyses

A comparison of the secondary endpoint, time on MV over 7 and 35 days follow-up, between treatment groups will be conducted only in participants that received MV.

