7.1.3 Trial participant exclusion criteria

- 1. Females who are pregnant, planning pregnancy or breastfeeding
- 2. Concurrent and/or recent involvement in other research or use of another experimental investigational medicinal product that is likely to interfere with the study medication within (specify time period e.g. last 3 months) of study enrolment
- 3. Serious condition meeting one of the following:
 - i. Respiratory distress with respiratory rate >=40 breaths/min
 - ii. oxygen saturation<=93% on high-flow oxygen
- 4. Require mechanical invasive or non-invasive ventilation at screening
- 5. Concurrent severe respiratory disease such as asthma, COPD and/or ILD
- 6. Any major disorder that in the opinion of the Investigator would interfere with the evaluation of the results or constitute a health risk for the trial participant
- 7. Terminal disease and life expectancy <12 months without COVID-19
- 8. Known allergies to dornase alfa and excipients
- 9. Participants who are unable to inhale or exhale orally throughout the entire nebulisation period

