11.3.4 Sensitivity and other planned analyses

All primary and secondary analyses will be repeated using the primary analysis population and the per protocol population. The use of the per protocol population is only as a sensitivity analysis to understand the impact of non-compliance.

This study utilises a combination of enrolled and randomised participants, historical controls and banked biosamples. Descriptive statistics will be produced for key baseline variables for all data sources within the comparator population. These will be used to evaluate the comparability of the source data.

There are planned subgroup analyses that relate to secondary objectives. A comparison of the secondary endpoint, time on MV, between treatment groups will be conducted only in participants that received MV. Other subgroup analyses may be performed but these are considered to be exploratory.

Further exploratory analyses are planned for the exploratory endpoints in the study. These analyses will follow the same principles and considerations with regards to the application of statistical approaches for specific data types and data structures. The exploratory analyses will use the exploratory analysis population.

Full details of the planned statistical analysis will be presented in a separate Statistical Analysis Plan (SAP). This will be finalised prior to database lock. The results from all analyses will be presented in the form of tables, figures and listings.

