## **Exploristics Limited**

# Identifier: EXP20012

Clinical Study Identifier: 132333 following Dexamethasone for HCs), whether they have a key comorbidity, defined as one or more of

hypertension, diabetes or cardiovascular disease as covariates and treatment included as covariates.

- Proportion of individuals on Mechanical Ventilation (MV) over 7 days follow-up
- Proportion of individuals on Mechanical Ventilation (MV) over 35 days follow-up
- Proportion of individuals with Pneumonia over 7 days follow-up
- Proportion of individuals with Pneumonia over 35 days follow-up

For the following secondary endpoints, a linear regression model will be fitted, with age, gender, BMI, baseline CRP (defined as the last CRP measurement prior to randomisation, or the first CRP following Dexamethasone for HCs), whether they have a key comorbidity, defined as one or more of hypertension, diabetes or cardiovascular disease as covariates and treatment included as covariates.

In addition, a supplementary analysis will be fitted for the length of ICU stay, a logistic regression model will be fitted, with a 1 for the outcome if the individual had any hours in the ICU and a 0 if the individuals had no hours in the ICU, with age, gender, BMI, baseline CRP (defined as the last CRP measurement prior to randomisation, or the first CRP following Dexamethasone for HCs), whether they have a key comorbidity, defined as one or more of hypertension, diabetes or cardiovascular disease as covariates and treatment included as covariates.

- Length of ICU stay (hours) over 7 days follow-up
- Length of ICU stay (hours) over 35 days follow-up
- Time on Oxygen over 7 days follow-up
- Time on Oxygen over 35 days follow-up
- Length of hospitalisation from baseline (days)

For the "time on Oxygen" analyses, regardless of the amount of oxygen received, if there is evidence that any oxygen was provided to the participant on that day, 24 hours will be added to the time on Oxygen.

For the following secondary endpoints, descriptive summary statistics only will be presented:

- Blood pressure over 7 days follow-up
- Pulse rate over 7 days follow-up
- Temperature over 7 days follow-up
- Respiratory rate over 7 days follow-up
- Time on MV over 7 days follow-up. This will only include individuals who were on MV at any point over 7 days follow-up.
- Time on MV over 35 days follow-up. This will only include individuals who were on MV at any point over 35 days follow-up.

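### Time on mechanical ventilation is contrasted only among ventilated patients, a subgroup formed after baseline, so selection bias can run either way and the SAP has no all-patient measure of MV duration

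*SAP*

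**What the plan says.** SAP 8.3.2 plans a comparison of time on MV over 7 and 35 days "between treatment groups will be conducted only in participants that received MV". Protocol 11.3.4 presents the same restriction as a planned subgroup analysis: "A comparison of the secondary endpoint, time on MV, between treatment groups will be conducted only in participants that received MV".

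SAP 11.2 repeats the restriction for each window ("This will only include individuals who were on MV at any point over 7 days follow-up" and "This will only include individuals who were on MV at any point over 35 days follow-up"), but places both under a different instruction: "For the following secondary endpoints, descriptive summary statistics only will be presented". So 8.3.2 announces a between-group comparison and 11.2 provides only summaries.

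Four other provisions bear on the point:

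- Protocol 7.1.3 excludes patients who "Require mechanical invasive or non-invasive ventilation at screening".
- SAP 11.2 fits logistic models to the proportion on MV at both windows (for example "Proportion of individuals on Mechanical Ventilation (MV) over 35 days follow-up") and analyses survival to Day 35, both in the primary analysis population.
- SAP 11.2 fits a linear model to length of ICU stay with no restriction to ICU patients, and adds a logistic model for any ICU stay.
- Protocol 11.1.2 lists time on MV as a continuous secondary outcome, and protocol 11.3.3 applies linear models to secondary endpoints in the primary analysis population.

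**The concern.** Receiving MV after entry is an outcome, and one the treatment is intended to influence: protocol section 3 gives fewer patients needing ventilatory support as an aim, and MV incidence is itself a secondary endpoint. Once the sample is cut to the ventilated, the randomised comparison loses its protection, and the matched historical controls are no longer matched within the subset. A difference in mean duration can then arise because different patients were ventilated, with no change in how long anyone stays on the ventilator.

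Death adds a second distortion. SAP 11.2 says how death is handled for time to discharge but gives no rule for time on MV, so a patient who dies soon after intubation contributes a short duration that looks favourable.

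The risk is a table of group means that readers take as a treatment effect on ventilation and that may point away from the true effect on total ventilation burden.

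**Working it through.** The documents give no planning figure for time on MV. The stated total of 90 is for CRP and has no bearing here.

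**Inputs from the documents.** Planned sizes are 30 active, 10 randomised to best available care (BAC) and 60 historical controls, so 70 controls (SAP 12). Protocol section 3 states that, of patients requiring oxygen, 25% need ICU, and that 47–71% of those need ventilatory support. This is background, not a planning rate: 0.25 × 0.47 = 11.75% and 0.25 × 0.71 = 17.75%.

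**Assumed, not in the documents.** Half of control courses last 3 days and half last 14. The drug averts half of one type and does nothing else. In the 7-day window, long courses are crudely capped at 7 days.

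**Formulas.** Ventilated-only mean = total MV days ÷ number ventilated. All-patient mean = total MV days ÷ all patients, with 0 for the non-ventilated.

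Per control-arm ventilation over 35 days:

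- Control: 0.5 × 3 + 0.5 × 14 = 8.5 MV days; ventilated-only mean 8.5.
- Half of short courses averted: 0.25 × 3 + 0.5 × 14 = 7.75 MV days over 0.75 ventilated; mean 7.75 ÷ 0.75 = 10.3.
- Half of long courses averted: 0.5 × 3 + 0.25 × 14 = 5.0 MV days over 0.75 ventilated; mean 5.0 ÷ 0.75 = 6.7.

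| Window | Courses averted | Ventilated-only mean, control → active | Total MV days, all patients |
|---|---|---|---|
| 35 days | half of short | 8.5 → 10.3 | 8.5 → 7.75 (−9%) |
| 35 days | half of long | 8.5 → 6.7 | 8.5 → 5.0 (−41%) |
| 7 days | half of short | 5.0 → 5.7 | 5.0 → 4.25 (−15%) |
| 7 days | half of long | 5.0 → 4.3 | 5.0 → 3.25 (−35%) |

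In every row the drug lowers total MV days and leaves each remaining course unchanged. The ventilated-only mean nevertheless moves up or down according to which courses were averted.

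**Per patient.** At MV rates of 11.75–17.75%, the first row gives 1.00–1.51 days in controls (8.5 × rate) and 0.91–1.38 on active (7.75 × rate).

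**Sensitivity of the first row.** Averting 25% of short courses gives an active mean of 9.3 days; averting all gives 14.0. With half averted and short courses making up 30% or 70% of the total, the means move from 10.7 to 12.1 and from 6.3 to 8.1.

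**Numbers in the contrast.** Controls: 70 × 0.1175 = 8.2 to 70 × 0.1775 = 12.4, of whom 1.2 to 1.8 are randomised BAC patients. Active: 30 × rate = 3.5 to 5.3, or 2.6 to 4.0 after a quarter of ventilations are averted.

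**Shift against noise.** The SD is 11 × √(0.5 × 0.5) = 5.5 in controls and 11 × √(1/3 × 2/3) = 5.19 on active. SE = √(5.5²/12.4 + 5.19²/4.0) = 3.0 days at the higher rate and √(5.5²/8.2 + 5.19²/2.6) = 3.8 at the lower. The 1.8-day shift is about 0.5 to 0.6 of a standard error.

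**The case against.** The strongest reply is that little rests on this summary. SAP 11.2 gives it no model, test or treatment estimate, and SAP 8.4 says that secondary endpoints are unpowered and handled descriptively. If the drug changed who is ventilated, the modelled proportion on MV in the full population is aimed at exactly that, with survival beside it. This stands and sets the weight of the point. It does not remove it: the proportion and the duration are never combined, and 8.3.2 still calls the ventilated-only contrast a comparison.

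Three stronger readings are tempting, and the documents do not support them.

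- A reader might infer that the analysis will make the drug look as if it prolongs ventilation. That needs short courses to be the ones averted; averting long courses moves the mean the other way. With so few ventilated patients, the illustrated shift is also within noise.
- A reader might infer that no all-patient analysis of MV duration was ever planned. Protocol 11.3.3 can be read as planning one, with 11.3.4 adding the ventilated subgroup. The gap is in the current SAP.
- A reader might infer that nobody in the analysis is ventilated at baseline. The exclusion applies at screening, and SAP section 5 applies the criteria to historical controls only where the data exist.

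**Conclusion.** The point holds as a modest, inexpensive improvement. The SAP's only summary of MV duration conditions on a post-baseline event, has no rule for death, and is described inconsistently in 8.3.2 and 11.2. The selection bias has no fixed direction: under the assumed durations the 35-day ventilated-only mean moves from 8.5 to either 10.3 or 6.7 days, while MV days over all patients fall by 9% or 41%. Those sizes rest on assumed durations and effects, and the counts of about 3 to 5 active and 8 to 12 control patients rest on background rates.

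This is not a route to a false significant result, since no test is planned, and it does not touch the primary CRP analysis. What is at stake is a misleading descriptive contrast. The SAP's unrestricted handling of ICU stay shows that an all-patient version fits its own approach.

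**What to change.** In SAP 2.2.2, 8.3.2 and 11.2:

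1. Report time on MV over 7 and 35 days in the whole primary analysis population, in one of two forms: MV days with 0 for non-ventilated patients, shown beside mortality; or days alive and free of MV, with death scored 0 and the components reported.
2. State the rule for unobserved days. Participants discharged before Day 35 have only a telephone call about breathing (protocol 8.4.1), and historical records may end before Day 35 (SAP 11.2). The SAP's audit trail also says that MV incidence could not be reliably inferred from the data, so complete MV days should not be taken for granted.
3. Keep the ventilated-only duration as a descriptive summary, explicitly labelled as not a treatment comparison and placed next to the proportion on MV.
4. Align SAP 8.3.2 and protocol 11.3.4 with the descriptive status in SAP 11.2.

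The cost is one extra table, an explicit assumption about unobserved days, component reporting if the composite is chosen, and a wording change in the protocol as well as the SAP.
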